### **4.2.2 Dosage, Administration, and Compliance**

#### **4.2.2.1 Olesoxime**

Olesoxime will be given as a 100-mg/mL liquid formulation. The drug will be administered at 10 mg/kg *BID* orally or via a naso-gastric or gastrostomy tube with *breakfast and dinner, preferably at the same time of the day throughout the study. If drug administration does not coincide with one of the scheduled meals, a snack should be taken prior to drug administration. Preferably there should be at least 10 hours between the morning and evening dose. The total daily dose in this study will not exceed 2000 mg. Therefore, patients with a body weight >100 kg will receive a dose of 1000 mg BID.*

*For the dose increase procedures of the patients who consent to Protocol BN29854, Version 4, please refer to Section 3.1.1.4.*

*Patients who do not consent to the dose increase will continue with the previous dosage and receive a dose of 10 mg/kg QD orally or via a naso-gastric or gastrostomy tube with the main meal, preferably at the same time of the day, throughout the study.*

Dose will be determined by weighing the patient at every visit (see Schedule of Assessments in [Appendix 1](#)), and recorded in the electronic Case Report Form (eCRF). Dose should be adjusted at every visit according to the weight changes.

In the event that the patient has to undergo medical procedures that impair the administration of study drug, sites can interrupt treatment at the discretion of the treating investigator. If interruption of treatment is prolonged (more than 8 weeks), the treating investigator should notify the Sponsor.

IMP administration should be recorded on the Study Drug Administration electronic Case Report Form (eCRF). Any overdose or incorrect administration of study drug should be documented in the patient's *diary* and recorded in the eCRF. Adverse events associated with an overdose or incorrect administration of study drug should be recorded on the Adverse Event eCRF.

#### **4.2.2.2 Treatment Compliance**

Patients will be asked to document drug administration in a patient diary. Compliance with study drug intake (dose, frequency, should be checked by the investigator at scheduled visits). The data from the patient's diary will be provided to the Sponsor.

#### **4.2.3 Investigational Medicinal Product Accountability**

The IMP, olesoxime, will be provided by the Sponsor. The study site will acknowledge receipt of IMP, using IxRS, to confirm the shipment condition and content. Any damaged shipments will be replaced.

At applicable sites, study drug may be shipped to patients home and receipt confirmed by a trained home nursing (HN) professional at the patient's home, if the patient has given written informed consent to participate in HN visits.

IMP will either be disposed at the study site according to the study site's institutional standard operating procedure or returned to the Sponsor with the appropriate documentation. The site's method of IMP destruction must be agreed by the Sponsor. The site must obtain written authorization from the Sponsor before any IMP is destroyed, and IMP destruction must be documented on the appropriate form.

Accurate records of all IMPs received at, dispensed from, returned to, and disposed of by the study site should be recorded on the Drug Inventory Log.

#### **4.2.4 Post-Trial Access to Olesoxime**

The Sponsor will offer post-trial access to the study drug olesoxime free of charge to eligible patients in accordance with the Roche Global Policy on Continued Access to Investigational Medicinal Product, as outlined below.

A patient will be eligible to receive study drug after completing the study if all of the following conditions are met:

- The patient has a life-threatening or severe medical condition and requires continued study drug treatment for his or her well-being
- There are no appropriate alternative treatments available to the patient
- The patient and his or her doctor comply with and satisfy any legal or regulatory requirements that apply to them

A patient will not be eligible to receive study drug after completing the study if any of the following conditions are met:

- The study drug is commercially marketed in the patient's country and is reasonably accessible to the patient (e.g., is covered by the patient's insurance or would not otherwise create a financial hardship for the patient).
- The Sponsor has discontinued development of the study drug or data suggest that the study drug is not effective for SMA.
- The Sponsor has reasonable safety concerns regarding the study drug as treatment for SMA.
- Provision of study drug is not permitted under the laws and regulations of the patient's country.

The Roche Global Policy on Continued Access to Investigational Medicinal Product is available at the following Web site:

[http://www.roche.com/policy\\_continued\\_access\\_to\\_investigational\\_medicines.pdf](http://www.roche.com/policy_continued_access_to_investigational_medicines.pdf)

#### **4.3 CONCOMITANT THERAPY AND FOOD**

Concomitant therapy includes any medication (e.g., prescription drugs, over-the-counter drugs, herbal or homeopathic remedies, nutritional supplements), as well as, e.g., prescribed exercise and physical therapy programs used or performed by a patient from at least 6 weeks prior to screening up to the study completion/discontinuation visit. All such medications and therapies should be reported to the investigator and recorded on the eCRF.

##### **4.3.1 Permitted Therapy and Medical Procedures**

Patients will be allowed to continue or start any symptomatic therapy or medical procedures needed to improve survival and quality of life, as judged by the treating physician. Dosing should always be used in the dose range according to the approved local prescribing information. Therapies for the treatment of SMA or agents anticipated to increase or decrease muscle strength are permitted, which include, but are not restricted to:

*Nusinersen (Spinraza®), riluzole, valproic acid, hydroxyurea, sodium phenylbutyrate, butyrate derivatives, growth hormone, anabolic steroids, probenecid, agents anticipated to increase or decrease muscle strength or presumed histone deacetylase inhibition activity*

*Use of nusinersen (Spinraza®) does not exclude patients from continued participation and treatment with olesoxime in Study BN29854.*

Patients should remain on stable dose throughout the study. However, in case it is medically recommended that a dose or therapy is modified, this should be recorded in the eCRF.

#### **4.3.1.1 Prohibited Therapy**

Use of the following therapies is prohibited during the study treatment:

- Investigational therapy
- Medications that could interfere with olesoxime absorption: ezetimibe, bile salts chelators (cholesteramine), fibrates, phytosterols
- Medication that could interfere with olesoxime pharmacodynamics: tamoxifen

#### **4.3.2 Food and Drink**

There are no specific dietary requirements or prohibited food in this study. The investigator may give or refer the subject for specific nutritional advice based on patients' health status. In case specific nutritional advice, such as enteric nutrition, is recommended, this should be recorded in the eCRF.

### **4.4 STUDY ASSESSMENTS**

Please see Appendix 1 for Historical Data Collection.

Laboratory safety samples should be collected first at each visit, *preferably* under fasted conditions. After receiving food, the PRO assessments (in the pre-specified order) should be administered first. Then, all other assessments can be performed in the order convenient for the site. If it is not possible for the patient to perform all assessments during the day, the site may divide the assessments between 2 consecutive days.

At applicable sites, certain study assessments may be performed by a trained home nursing professional (HN) at the patient's home to improve access and convenience for patients participating in the study. The schedule of assessments (see [Appendix 1](#)) will specify the assessments that may be performed by an HN professional.

#### **4.4.1 Informed Consent Forms and Screening Log**

Written informed consent for participation in the study must be obtained from the patient, parent or legal guardian and if appropriate, assent from the child, before any study-specific screening tests, Historical Data Collection or evaluations are performed. The study can have two main Informed Consent Forms signed from each patient: one for providing detailed historical information (Historical Data Collection), and one for the open-label period of this study. However, participation in one part of the study does not preclude or oblige the patient to participate in the other part of the study. For the Caregiver Reported Outcomes, written informed consent must be obtained from the the caregiver (please refer to Section [4.4.11](#)). The signed Informed Consent Forms will be maintained at the study site.

All screening evaluations must be completed and reviewed to confirm that patients meet all eligibility criteria before initiation of treatment with olesoxime. The investigator will maintain a screening log to record details of all patients screened and to confirm eligibility or record reasons for screening failure, as applicable.

#### **4.4.1.1 *Informed Consent Form for Protocol BN29854, Version 4***

*All patients, or if appropriate, legal guardians, must have signed informed consent for the new schedule of assessments and related procedures (see Section 3.1.1.4). If the patient agrees to the 10 mg/kg BID dose, as well as all procedures and assessments per Protocol BN29854, Version 4, this must be documented in the informed consent.*

*In case the patient or his/her caregiver initially declines receiving the dose increase and subsequently reconsiders the decision, new written informed consent must be obtained.*

#### **4.4.2 Historical Data Collection**

Historical Data Collection includes any clinically significant diseases and medical complications that in the opinion of the treating investigator are related to the natural course of SMA (for instance, but not restricted to, pulmonary, gastrointestinal, orthopedic, nutritional), medical procedures (such as, but not restricted to, scoliosis surgery, gastrostomy feeding, use of ventilation, history of pulmonary infections/events), and its treatments used by the patient from the last visit in study TRO19622CLEQ1275-1 or TRO19622CLEQ1115-1 up to the screening visit for study BN29854.

Further information requested will be patient clinical status during routine clinical visits, that may include any SMA validated motor functional scale, such as the MFM and HFMS, and/or disability scale (e.g., Brooke, Vignos) performed during the above mentioned period.

The information will be collected at screening from patients who consent ([Appendix 2](#)).

**NB** The Historical Data Collection requires a separate informed consent.

#### **4.4.3 Medical History and Demographic Data**

Demographic data and other applicable medical history will be collected at screening to verify patient's eligibility. Demographic data will include age, sex, and self-reported race/ethnicity, education status, and employment status (if applicable).

Other applicable medical history will include reproductive status, smoking history, use of alcohol and drugs of abuse and all medications (e.g., prescription drugs, over-the-counter drugs, herbal or homeopathic remedies, nutritional supplements) and medical procedures not related to SMA in the opinion of the treating physician.

**NB** For other applicable medical history, patients should have provided informed consent for the open-label treatment period of the study.

#### **4.4.4 Anthropometric Measurements**

Anthropometric measurements include body weight at every visit, and height at baseline, and every 6 months thereafter *as well as at a possible early discontinuation visit*.

The patient's body weight will be measured to the nearest kilogram using a calibrated scale. For wheelchair-bound patients, weight of the patient will be obtained with a wheelchair balance scale with the patient in the wheelchair. The wheelchair should be also weighed by itself and subtracted from total weight.

The patient's height will be measured or derived *from ulna length* to the nearest centimeter.

Ulna length (from the tip of the olecranon process to that of the styloid process) will be measured using an anthropometer with the patient in sitting position, the left forearm resting comfortably on a table, elbow bent 90 to 110, palm facing downwards and fingers extended but together.

The assessments will be performed as in the Schedule of Assessments [Appendix 1](#), and the formula for calculation of BMI is provided in [Appendix 4](#).

#### **4.4.5 Physical Examinations**

A complete physical examination should be performed at screening including the evaluation of the head, eyes, ears, nose, and throat, and the cardiovascular, dermatological, musculoskeletal, respiratory, gastrointestinal, genitourinary, and neurological systems. Any abnormality identified at screening or baseline should be recorded on the General Medical History and Baseline Conditions eCRF.

At baseline and subsequent visits (or as clinically indicated), limited, symptom-directed physical examinations should be performed. Changes from baseline abnormalities should be recorded in patient notes. New or worsened clinically significant abnormalities should be recorded as adverse events on the Adverse Event eCRF.

#### **4.4.6 Vital Signs**

Vital signs will include measurements of temperature, respiratory rate, pulse rate, and systolic and diastolic blood pressure (BP) while the patient is in a seated position, after the patient has rested for approximately 5 minutes. BP measurements should be done at the same arm and with the same cuff size using an automatic instrument with a digital readout throughout the study.

Vital signs should be measured prior to blood draw or at least 10 minutes after the last blood draw.

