### **Length of Study**

The study will continue until olesoxime is commercially available in the patient's country, or as per local regulation, or per the Sponsor's decision to terminate the olesoxime program for SMA, but will not exceed 4 years after the last patient was enrolled in the study.

**NB** In the UK, the study will last for a fixed period of 3 years.

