### **1.2.2 Study TRO19622CLEQ1275-1**

*Study TRO19622CLEQ1275-1 was a Phase II/III, adaptive, parallel-group, double-blind, randomized, placebo-controlled, multicenter, multinational study designed to assess the efficacy and safety of olesoxime over 24 months in pediatric and adult patients (3–25 years of age) with Type 2 and non-ambulatory Type 3 SMA.*

There were 165 patients randomized in a 2:1 ratio to olesoxime 10 mg/kg QD or placebo. The first patient was enrolled on 18 November 2010, and the last patient, last visit occurred in October 2013.

The primary outcome measure was the Motor Function Measure (MFM), which is a multidimensional motor function scale for use in patients with neuromuscular disorders. The MFM has been validated in SMA and has been divided into three sub-domains: D1, which evaluates functions related to standing and transfer; D2, which evaluates axial and proximal function in supine and sitting positions on a mat and a chair; and D3, which evaluates distal motor function (Bérard *et al.* 2005). As SMA primarily affects proximal muscles, the primary endpoint of the study was change from baseline at Month 24 in the MFM D1 + D2 score. The result for the primary outcome was in favor of olesoxime and close to statistical significance when compared with placebo (treatment effect: 2.0 [96% CI: -0.25, 4.25];  $p=0.0676$ ) (Bertini *et al.* 2017).

The secondary endpoints included the MFM Total score (D1+D2+D3), the Hammersmith Functional Motor Scale (HFMS), and a responder analysis on both functional motor scales. Electromyography (maximum compound muscle action potential [CMAP] / motor unit number estimation [MUNE]), Forced Vital Capacity (FVC), Pediatric Quality of Life Inventory™ (PedsQL™), Clinical Global Impression (CGI), and safety were formally tested using analysis of covariance (ANCOVA) or other methods. The magnitude of the treatment effect based on the total MFM score (D1+D2+D3) was quite similar to the D1+D2 analysis. The change in HFMS after 21 months treatment showed a positive trend for the olesoxime treatment arm over time.

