The PK and efficacy data from Study TRO19622CLEQ1275-1 were used to investigate the relationship between olesoxime PK exposure (i.e., average trough concentration [ $C_{average}$ ]) and the primary efficacy outcome (i.e., MFM D1 + D2 score). The results of this analysis indicated that the effect of olesoxime did not reach a plateau at the dose of 10 mg/kg QD and that higher doses may lead to an increase in efficacy (see PK/pharmacodynamic [PD] report) (see Section 3.3.1).

Baseline samples from 119 patients previously enrolled in Study TRO19622CLEQ1275-1 (81 patients in olesoxime arm and 38 patients in placebo arm) were analyzed. All patients previously on olesoxime in Study TRO19622CLEQ1275-1 had detectable predose olesoxime concentrations at baseline of Study BN29854. Olesoxime concentrations ranged from 23 to 801 ng/mL, corresponding to 0.3% to 9.5% of  $C_{average}$  observed in Study TRO19622CLEQ1275-1. The time after last dose from Study TRO19622CLEQ1275-1 was 2.4–4.0 years. Olesoxime was not detected in the OLEOS baseline samples from any of the 38 patients previously randomized to placebo arm in Study TRO19622CLEQ1275-1. Roche currently assumes that these residual concentrations are secondary to the accumulation of olesoxime, a cholesterol derivative, in a deep compartment.

Based on currently available data, residual exposure to olesoxime for periods up to 6 years does not appear to be associated with any newly emerging safety risks.

Study TRO19622CLEQ1275-1 indicated that treatment with olesoxime maintained motor function in SMA Type 2 and non-ambulatory Type 3 patients, as measured by the MFM, and decreased disease-related complications.

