## **3.2 END OF STUDY**

*The study will continue until olesoxime is commercially available in the patient's country, or as per local regulation, or per the Sponsor's decision to terminate the olesoxime*

program for SMA, but will not exceed 4 years after the last patient was enrolled in the study.

**NB** In the UK, the study will last for a fixed period of 3 years.

The end of this study is defined as the date when the last patient, last visit (LPLV) of the treatment period occurs.

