## **6.6 PRIMARY ANALYSES**

Safety analysis will be based on the safety population.

Safety variables (e.g., laboratory tests, vital signs, and ECG) will be summarized for each assessment time (including follow-up) using descriptive statistics. *The data will be summarized by the dose being taken at the time of the assessment (10 mg/kg QD or 10 mg/kg BID). Data from the two 24-hour Holter ECG assessments will also be summarized.*

Adverse events will be coded and summarized by body system and preferred term. Adverse events will also be summarized by intensity and relationship to trial treatment as assigned by the investigator. Serious adverse events will be summarized separately. *Adverse events will be summarized by the dose being taken at the onset date of the adverse event.*

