4.6.5 Vital Signs

Vital signs assessments, including temperature, respiratory rate, pulse rate, blood pressure, weight, height and BMI will be measured throughout the study. If height cannot be measured directly, ulnar length will be used to calculate a surrogate height measure as described in Section 4.3.1. Summaries for vital signs will be presented at each time-point for actual values and change from baseline values. Percentiles for

weight-for-age, stature-for-age, weight-for-stature and BMI-for-age and change from baseline percentiles will also be presented for all patients.

Vital signs data will be listed for patients with values outside the normal ranges for temperature, respiratory rate, pulse rate, systolic blood pressure and diastolic blood pressure. The normal ranges will be based on the age of the patient at the time of the assessment. In addition, shift tables to compare the status at baseline to each time-point post-baseline and overall will be presented. The following normal ranges will be used:

Age (months)	Heart/Pulse Rate (beats/min)	Respiratory Rate (breaths/min)	Systolic Blood Pressure (mmHg)	Diastolic Blood Pressure (mmHg)	Temperature (°C)
>24 and ≤144		18-30	80-125	40-80	35.5-37.8
>144	50-100	12-20	90-140	40-120	36.5-37.5
>72 and ≤96	60-110				
>96 and ≤144	55-100				

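### Protocol 4.4.6 keeps one blood pressure cuff size for a multi-year study that includes growing children, and does not provide for refitting the cuff or recording its size

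*Protocol*

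**What the plan says.** Protocol 4.4.6 (Vital Signs) states that blood pressure measurements "should be done at the same arm and with the same cuff size using an automatic instrument with a digital readout throughout the study". This is the only cuff instruction in either document.

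Protocol 3.2 says the study "will not exceed 4 years after the last patient was enrolled in the study", with a fixed 3 years in the UK. The main feeder study, described in Protocol 1.2.2, enrolled "pediatric and adult patients (3–25 years of age) with Type 2 and non-ambulatory Type 3 SMA". For the patients sampled at baseline of the present study, "The time after last dose from Study TRO19622CLEQ1275-1 was 2.4–4.0 years".

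The protocol expects patients to grow. It plans yearly Tanner staging at ages 9-17 (4.4.7), height every 6 months (4.4.4) and a dose re-set to body weight at every visit (4.2.2.1).

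Vital signs are part of the primary objective (Protocol 2.1). SAP 4.6.5 states: "Summaries for vital signs will be presented at each time-point for actual values and change from baseline values". It adds shift tables against normal limits chosen by the patient's age at the assessment. Protocol 6.6 adds that safety data are summarized by the dose in use at the assessment, QD or BID.

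**The concern.** Keeping the arm, device and cuff constant is meant to reduce measurement noise. That works in adults. In a growing child, a constant cuff size means a changing fit. A cuff that has become too small for the arm is generally held to over-read, so the rule can put a within-patient trend into the variable it is meant to standardize.

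The planned displays would carry this trend through, because they compare each patient with his or her own baseline. The study has no concurrent control, and neither document plans a correction for cuff fit. The age-based limits in SAP 4.6.5 change the threshold, not the reading. Without a recorded cuff size, nobody could later identify which readings were affected.

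For patients who accept the dose increase, QD comes first and BID later. Any growth-related error therefore falls more heavily on the BID side of a by-dose table.

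**Working it through.** **Step 1: is there an exception elsewhere?** Protocol 4.4.4 (body measurements), the Appendix 1 footnote on vital signs and SAP 4.6.5 were compared with Protocol 4.4.6. None permits a change of cuff. None asks for arm circumference or cuff size.

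**Step 2: how young are the patients, and for how long would one cuff be used?** Inputs are the feeder-study entry age of 3-25 years, its 24-month treatment period, and 2.4-4.0 years since the last dose (all Protocol 1.2.2). For patients who completed 24 months:

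- Youngest at baseline: 3 + 2 + 2.4 = 7.4 years.
- Oldest at baseline: 25 + 2 + 4.0 = 31.0 years.
- Youngest at Week 156: 7.4 + 156/52.18 = 10.4 years.
- Youngest at Week 208: 7.4 + 208/52.18 = 11.4 years.

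These are limits, not a distribution. They show that one cuff size could stay in use through 3-4 years of growth in the youngest patients, and that the cohort also includes adults.

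**Step 3: effect on the mean.** The documents give no figure, so both inputs are assumptions: 20-50% of patients outgrow the cuff, and each then reads 2-10 mmHg too high.

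Mean shift = share affected × error per affected patient.

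- Low end: 0.20 × 2 = 0.4 mmHg.
- Middle: 0.35 × 5 = 1.75 mmHg.
- High end: 0.50 × 10 = 5 mmHg.

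**Step 4: effect on the systolic limits.** SAP 4.6.5 uses an upper limit of 125 mmHg up to 144 months of age and 140 mmHg above that. Assume a true systolic mean of 110 and SD of 10 mmHg, normally distributed, with no drug effect. Share above the limit = 1 − Φ((limit − 110 − error)/10).

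| Assumed error (mmHg) | Above 125 (age ≤144 months) | Above 140 (age >144 months) |
|---|---|---|
| 0 | z = 1.5: 6.7% | z = 3.0: 0.13% |
| +3 | z = 1.2: 11.5% | z = 2.7: 0.35% |
| +5 | z = 1.0: 15.9% | z = 2.5: 0.62% |
| +10 | z = 0.5: 30.9% | z = 2.0: 2.3% |

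The table applies only to patients whose arm has outgrown the cuff.

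**Step 5: which column applies in the BID period?** The feeder study's last visit was in October 2013, so 24-month completers had entered by about October 2011. Protocol 1.2 reports the state of development as of September 2017, so Version 4 is no earlier than that. The interval is at least 5 years 11 months, about 5.9 years. A patient still aged 12 or under at the start of BID must have entered the feeder study at about 12 − 5.9 = 6.1 years or younger. From an entry range of 3-25 years, most patients would face the 140 mmHg limit by then.

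A child who passes 144 months gains 140 − 125 = 15 mmHg of systolic and 120 − 80 = 40 mmHg of diastolic headroom. Both exceed the largest error assumed here.

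**The case against.** **Wording and mechanism.** The protocol says should, not must, and a constant arm, cuff and device is a deliberate standardization. The direction of the error comes from outside the documents. Height and weight are not arm girth, and Protocol 1.1 describes muscle wasting that is mainly proximal, so outgrowing the cuff cannot be assumed for every child. All of this stands and limits the size of the point. It does not supply a rule for the child whose arm does outgrow the cuff.

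**The 125 mmHg figures.** A reader might infer that up to about 31% of patients would be wrongly flagged as high in the BID period. The documents do not support that: the 125 mmHg limit stops at 144 months, and most patients would be past it when BID starts.

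**Attribution to the dose increase.** A reader might also infer that cuff drift would by itself create a false BID effect. That goes too far. Blood pressure generally rises with age, so QD versus BID is confounded with age and calendar time even with a perfect cuff. Patients who decline the increase stay on QD and would carry the same drift into the QD column. No hypothesis test is planned. The SAP describes once-daily dosing only (sections 2 and 3.1), so the by-dose display rests on Protocol 6.6. The cuff rule adds an avoidable error to a comparison that is already weak.

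**Remedy.** Excluding visits where the cuff differs from baseline would discard correctly measured readings from the growing patients. A new rule introduced with Version 4 could also produce a downward step close to the start of BID. Both objections are right and shape the fix below.

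**Unverifiable part.** The eCRF is not among the documents, so it cannot be checked whether it already has a cuff-size field.

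**Conclusion.** The point holds in a limited form. Followed as written, Protocol 4.4.6 leads to badly fitting cuffs in some growing patients, and neither document provides a way to detect this afterwards. The affected readings feed the change-from-baseline and shift summaries of a primary-objective safety variable, mainly at later visits.

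The documents do not establish the size. On the stated assumptions the later mean shifts by 0.4-5 mmHg. The upper end needs both half the cohort affected and the largest error, so the effect on the overall mean is probably small. Adults are largely unaffected. The effect on the share above the systolic limit is material only for affected children up to 144 months. Above that age it stays at or below about 2.3% on the same assumptions. The documents do not support a claim that the rule would manufacture, or conceal, a blood pressure effect of the BID dose. The change is worth making because it is cheap and the missing information cannot be recovered later.

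**What to change.** **Protocol 4.4.6.** Keep the same arm and the automatic instrument. Replace the constant cuff size with a cuff size that fits the arm at that visit, and record the size used at each measurement. Apply this to home-nursing visits too, since Appendix 1 lets the home nurse take vital signs.

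**SAP 4.6.5.** Keep visits with a changed cuff in the main summaries and flag them. Add one display of blood pressure change from baseline, split by whether the cuff size changed. Read it descriptively: patients whose cuff changed are the growing ones, whose true pressure is also likely to rise.

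**Timing.** State the date the rule took effect at each site and show it beside the by-dose summaries, because a step in readings may coincide with the start of BID. Cuff sizes used before that date may not be recoverable, and the report should say so.

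**Cost.** One protocol sentence, one eCRF field if none exists, one extra table and a footnote. The price is a possible visible step when a cuff is changed. The recorded size and date make the step traceable.
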